### **3.4 Screening and Eligibility Criteria**

All pediatric patients who admitted to the ICU at a study hospital site with a TBI are screened and their families/guardians are approached to enroll. Patients who are not eligible at admission but deteriorate are included at the time deterioration is assessed. No other exclusions.

To be included the patient must be:

- Age < 18 years
- Mechanism or CT evidence of TBI
- Glasgow Coma Scale (GCS) Score  $\leq 8$  (if intubated, motor GCS  $\leq 5$ )
- Admitted to ICU at any point in the hospital stay

An enrollment log will be kept in the secure database. Reasons for non-enrollment (does not meet eligibility criteria, death before consent, consent refusal, withdrawal) will be documented.

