### **3.8 Recruitment, Retention & Follow-up**

Recruitment is limited to eligible patients admitted and consented at study sites. Based on baseline recruitment levels, the target sample size of 432 is feasible with about 9 participants per site per year. This is an in-patient intervention for the first 7 days of ICU care where intervention ICU staff are trained on intervention delivery as part of their patient care. Other data will be obtained from the health records. Follow-up data collection will be attempted at three months post-admission and can be completed in-person, via telephone, or from the health record. If unable to complete follow-up by four months, the participant will be designated lost-to-follow-up, but in-hospital data will be included. There is no incentive for participation offered to patients at any stage.

[figure not shown]

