## Analysis plan Aim 1A \_ PEGASUS Argentina \_ 031022

**Paper title:** TBD

**Specific Aim 1:** Determine the relationship between PEGASUS program implementation and TBI guideline adherence (Aim 1a)

*Hypothesis: Centers that receive the PEGASUS program have higher TBI guideline adherence (main outcome), as well as better discharge survival and 3-month Glasgow Outcome Scale-Extended (GOSE) score (secondary outcomes) than centers who receive usual care.*

**Authors:** TBD

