**Questions of interest:**

- 1) Does PEGASUS implementation improve guideline adherence?
- 2) Are there any imbalances between the study arms that need to be addressed?

**Study Design:** 2-arm parallel cluster RCT

**Study population:** Pediatric (<18) ICU patients with severe TBI at 16 sites

**Exposure variable(s):** Study Arm (binary)

**Outcome variable(s):** (1) TBI guideline adherence

*"The main outcome is TBI guideline adherence during first 3 days ICU stay, calculated via our previously developed TBI guideline adherence scorecard. Using patient charts, we measure presence or absence of adherence to the indicators and capture time since injury for any observed indicators, including the main protective KPIs (ventilation, nutrition, CPP). Patient guideline adherence is defined as the sum of indicators to which care was adhered divided by the number of relevant adherence indicators for a given patient. Mean adherence scores are calculated for each site individually and across all sites."*

Describe:

- (2) Extracranial injuries
- (3) Discharge GOS
- (4) Discharge survival
- (5) 3-month GOSE-Peds
- (6) 3-month mortality
- (7) KPIs?

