**Methods:**

1. Descriptive statistics for all measures at the facility level, within treatment and control arms. Potential differences in patient (age, sex, race/ethnicity) and injury characteristics will be examined using bivariate analyses by center using  $\chi^2$  tests (categorical) and t-tests (continuous).
2. ITT analysis: multi-level mixed effects Poisson regression with robust variance estimation and clustering by site to estimate the relative risk of PEGASUS implementation on TBI guideline adherence and stratified by extracranial injury, as described in Zou, et al.  
Per protocol: As with ITT, but potentially including implementation dose/fidelity as covariate and interaction with intervention.
3. Secondary analyses (Following ITT for primary analysis): Poisson regression with robust variance estimation and clustering by site to estimate separately the relative likelihood of program implementation on these outcomes: 1) in-hospital mortality; and 2) GOSE-Peds at 3 months post TBI, analyzing GOS score as a dichotomous measure (minor-moderate impairment vs major impairment-vegetative state and death).  
Multivariable Cox regression model to examine the marginal effect of PEGASUS on mortality during the 3 months post discharge, averaged over all centers.
4. Sensitivity analyses: repeated analysis on ICP monitoring patients
5. Subgroups: COVID effect and geographic effect

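### The Cox mortality model runs from discharge while follow-up runs from admission; as written it omits in-hospital deaths, and no planned model estimates the effect on all deaths by 3 months

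*SAP*

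**What the plan says.** SAP Methods item 3 opens "Secondary analyses (Following ITT for primary analysis" and then plans three models.

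- A Poisson model for in-hospital mortality.
- A Poisson model for "GOSE-Peds at 3 months post TBI, analyzing GOS score as a dichotomous measure", split as "minor-moderate impairment vs major impairment-vegetative state and death".
- A "Multivariable Cox regression model to examine the marginal effect of PEGASUS on mortality during the 3 months post discharge, averaged over all centers".

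Protocol 3.8 uses a different clock: "Follow-up data collection will be attempted at three months post-admission". A participant whose follow-up is not complete by four months is classed as lost.

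The SAP's outcome list includes "6) 3-month mortality" among the items to be described, and the SAP's list of potential products includes a Cox figure for 3-month mortality. Neither entry gives a time origin, so they are ambiguous rather than contradictory. The Aim 1 hypothesis is that PEGASUS centers have "better discharge survival and 3-month Glasgow Outcome Scale-Extended (GOSE) score".

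**The concern.** A survival clock that starts at discharge can only put at risk children who leave hospital alive. Survival to discharge occurs after the sites were randomised, and the SAP's own hypothesis expects PEGASUS to change it. If it does, the children discharged alive in the two arms need not be comparable, and randomisation does not protect the post-discharge contrast, even though the item is labelled as following ITT.

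The remaining models do not fill the gap. One stops at discharge; the other counts deaths only when pooled with severe disability. A reader shown a Cox figure described as 3-month mortality could take it for the effect on all deaths by 3 months, when it would show only deaths among children discharged alive.

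**Working it through.** **Setting the clocks side by side**

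| Item | Starts at | In-hospital deaths |
|---|---|---|
| Cox model (SAP Methods 3) | discharge | left out |
| In-hospital mortality (SAP Methods 3) | not stated; ends at discharge | counted; later deaths left out |
| GOSE-Peds split (SAP Methods 3) | TBI | counted, but pooled with major impairment |
| Follow-up contact (Protocol 3.8) | admission | not applicable |
| 3-month mortality in the SAP outcome and product lists | not stated | not stated |

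No row gives a model for death from any point of the stay through 3 months.

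**Can the planned follow-up supply the discharge clock?** Take 3 months as 91 days and 4 months as 122 days. Lengths of stay are assumed, because the documents give none. The window ends on day (stay + 91) after admission, and a contact on day 91 covers (91 − stay)/91 of it.

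| Assumed stay (days) | Window ends (day) | Covered by day-91 contact |
|---|---|---|
| 7 | 98 | 84/91 = 92% |
| 21 | 112 | 70/91 = 77% |
| 30 | 121 | 61/91 = 67% |
| 45 | 136 | 46/91 = 51% |
| 60 | 151 | 31/91 = 34% |

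For stays beyond 122 − 91 = 31 days, the window closes after the protocol's four-month cut-off.

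**The plan's own figure.** Protocol 3.7 gives no event count or hazard ratio for mortality; its one computed figure is 432. With 58.6% against 77.3% (18.7 read as percentage points), two-sided alpha 5%, 80% power and unpooled variance, n = 93.84 per arm before clustering. With 432/16 = 27 per site and an ICC of 0.05, the design effect is 1 + 26 × 0.05 = 2.3. Then 93.84 × 2.3 × 2 = 431.7, which rounds to 432. The figure reproduces, and the same design effect is used below.

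**How many deaths would the model use?** These rates are assumptions: 15–35% of 432 die by 3 months, and 5–30% of those deaths follow discharge.

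- All deaths: 432 × 0.15 = 64.8 to 432 × 0.35 = 151.2, so 65–151.
- Events in the model as written: 64.8 × 0.05 = 3.2 to 151.2 × 0.30 = 45.4, so 3–45.
- Deaths left out: 64.8 × 0.70 = 45.4 to 151.2 × 0.95 = 143.6, so 45–144 (70–95% of all deaths).

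A second set of assumptions takes in-hospital mortality of 10–30% and mortality of 1–3% among those discharged.

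- In-hospital deaths: 432 × 0.10 = 43 to 432 × 0.30 = 130.
- Highest share of deaths used: (432 − 43.2) × 0.03 = 11.7 events; 11.7/(43.2 + 11.7) = 21%.
- Lowest share used: (432 − 129.6) × 0.01 = 3.0 events; 3.0/(129.6 + 3.0) = 2%.

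Under both sets the model uses a minority of the deaths.

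**Precision.** With equal arms, the 95% CI for the hazard ratio is the estimate multiplied or divided by exp(1.96 × √(4 × D/events)), where D is the design effect.

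| Model | Events | D = 1 | D = 2.3 |
|---|---|---|---|
| As written | 3 | 9.6 | 31 |
| As written | 45 | 1.8 | 2.4 |
| All deaths | 65 | 1.6 | 2.1 |
| All deaths | 151 | 1.4 | 1.6 |

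The ICC of 0.05 was stated for adherence; applying it to mortality is a further assumption. For the model as written, 2.3 is slightly high because fewer children per site are at risk, and at 3 events the formula is only a rough guide.

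**The case against.** The phrase may be a drafting slip. Neither the outcome list nor the product list mentions discharge, and if admission was meant, the survivor selection and the omitted deaths disappear. That is possible, but the Methods sentence is the only one that specifies the model. An analyst following it would fit the wrong comparison, so the text needs correcting either way.

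The two secondary outcomes in the hypothesis, discharge survival and 3-month GOSE, each have a model that counts in-hospital deaths, so the Cox model is supplementary. This is true and limits the damage. It does not make the Cox result interpretable as 3-month mortality.

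The GOSE-Peds clock concerns a different outcome, and nothing shown here depends on the gap between injury and admission. That stands: the conflict with consequences is discharge against admission.

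The event ranges rest wholly on assumed rates, and precision is secondary to the question of what is being estimated. That also stands; the ranges illustrate scale and say nothing about bias.

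An admission clock brings its own problem. Children who die before consent are not enrolled, so the time from admission to consent is immortal. Entering patients at consent deals with the immortal time but still conditions on surviving to consent, which also follows site randomisation. Reporting those deaths by arm discloses this without removing it.

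**Conclusion.** The concern holds. As written, the Cox model excludes in-hospital deaths, compares groups selected on an outcome the intervention is expected to affect, and runs past the protocol's follow-up contact. No planned model estimates the effect of PEGASUS on all deaths by 3 months. On the first set of assumed rates it would leave out 70–95% of deaths.

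The wording mismatch is certain. The consequences depend on the sentence being implemented literally, and no size or direction of bias can be given from the documents. The reach is limited to a secondary outcome that Protocol 3.7 already calls insufficiently powered; an all-deaths model would remain imprecise. The adherence analysis and the sample size of 432 are untouched. It should be corrected because it is cheap to do so and decides what a reported mortality result means.

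**What to change.** In SAP Methods item 3, define the outcome as death from any cause through 3 months post-admission in all enrolled patients, and:

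- count in-hospital and later deaths alike;
- censor at 3 months post-admission or the date last known alive, and account for clustering by site;
- let patients enter the risk set at consent, either by delayed entry on the admission clock or by setting time zero at enrolment;
- report deaths before consent by arm from the enrolment log, where Protocol 3.4 says "Reasons for non-enrollment (does not meet eligibility criteria, death before consent, consent refusal, withdrawal) will be documented";
- name the covariates. The SAP's general list includes LOS but does not say what enters this model; LOS and anything else arising after time zero should stay out;
- use the same definition for the 3-month mortality outcome and the Cox figure.

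If a post-discharge analysis is wanted as well, label it descriptive and conditional on survival to discharge.

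The cost is a rewrite of one SAP item and little extra analysis. The Cox version needs dates of consent and of post-discharge death, which the available text does not mention (the data collection timeline figure is not shown). If dates of death were not recorded, analyse 3-month mortality as a binary outcome with the Poisson model already planned, and state how unknown vital status is handled. That needs only the 3-month vital status that the existing outcomes already require.

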**Potential products:**

- a) Descriptive table
- b) Outcome table
- c) Figure showing 3-month mortality in Cox model
- d) Figure showing variation in intervention dose/fidelity within and between sites
